4.12.3 Clinical Laboratory Evaluation

Blood samples for determination of clinical chemistry and haematology will be taken at the visits indicated in the SoA (see protocol). Additional safety samples may be collected if clinically indicated at the discretion of the investigator. The date, time of collection and results (values, units and reference ranges) will be recorded on the eCRF.

The clinical chemistry and haematology will be performed at a local laboratory at or near to the investigator site. Sample tubes and sample sizes may vary depending on laboratory method used and routine practice at the site.

In case of BLQ values (eg “<5”, “<100”) for some assessments, the following rule will be considered:

- If less than 50% of the assessments (across patients) are BLQ such as “<XXX”, then “XXX/2” will be considered for summaries.

- If 50% or more than 50% of assessments (across patients) are BLQ such as “<XXX” then “0” will be considered for summaries.

The following laboratory variables will be measured:

- Haematology (whole blood): Haemoglobin (Hb), Lymphocytes (absolute count and %), Neutrophils (absolute count and %), Platelet count, Total white cell count. . .
- Clinical Chemistry (serum or plasma): Albumin, Alanine transaminase (ALT), Alkaline phosphatase (ALP), Amylase (only for arm B), Aspartate transaminase (AST), Calcium, Calcium corrected, Creatinine, CRP, Glucose, Lactate dehydrogenase (LDH), Lipase (only for arm B), Magnesium, Phosphate, Potassium, Sodium, Total bilirubin, Urea. . .

The original lab test units will be converted using the International System of Units (SI) [11].

Laboratory test with numerical grading criteria in the NCI CTCAE v5.0 will be graded accordingly. Grade 0 will be assigned for all non-missing values not graded as 1 or higher. For laboratory tests where grades are not defined by CTCAE v5.0 results will be classified as low, normal or high based on laboratory normal ranges.

The following summaries will be provided for all parameters for arm A and arm B:

- A summary of results by assessment visit (as per SoA)
- Shift tables will be provided for all parameters to compare a patient’s baseline laboratory grade relative to worst post-baseline grade (Low and/or High abnormal direction will be considered for each parameter).

By-patient listing will be provided for all patient in FAS by arm and visit, including changes from baseline, grade and reference range. All values outside the clinical reference ranges will also be flagged in the data listings. The abnormal values will be flagged with ‘L’ for values below the lower limit of the clinical reference range and ‘H’ for values above the upper limit of the clinical reference range. In addition, box plots presenting the results per visit will be presented for each lab parameters.

eDISH plots will also be produced to assess the liver toxicity.

4.12.4 Vital Signs, Physical Examinations and Other Observations Related to Safety

4.12.4.1 Vital Signs

The following vital signs will be recorded at baseline and post-baseline visit:

- Weight (kg)
- Systolic blood pressure (in mmHg)

- Diastolic blood pressure (in mmHg)
- Pulse rate (beats/minute)
- Temperature (°C or °F)
- Respiratory rate (breaths per minute)

A shift table from baseline systolic blood pressure and diastolic blood to worst on-treatment results will be presented. The normal/abnormal classification will be made using the criteria defined in table below:

Table 2 – Vital Sign Criteria for Abnormalities

Vital Sign Criteria for Abnormalities	Criteria for Abnormalities (any of the following situation)
Systolic blood pressure	
 - value <80 mmHg - value >129 mmHg
Diastolic blood pressure	
 - value <60 mmHg - value >80 mmHg

Vital signs data and clinically relevant abnormalities in vital signs will also be listed.

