**Table 14 Dose Modification and Stopping Criteria**

Event	Action
Colitis events (e.g. Colitis, ileitis, enterocolitis etc)	
Grade 1	If receiving RXC004, either as monotherapy or in combination with nivolumab; Reduce RXC004 to a lower dose (see Table 15 for dose reduction scheme) and manage as per Appendix J (and Appendix G if applicable)
Grade 2	If receiving RXC004, either as monotherapy or in combination with nivolumab Interrupt RXC004. Manage as per Appendix J and Appendix G if applicable. When event has resolved to Grade 1 a and steroids tapered to $\leq 10$ mg of prednisone per day (or equivalent), resume RXC004 at a lower dose (see Table 15 for dose reduction scheme) and nivolumab (if applicable) at 480 mg q4w. If event re-occurs after re-starting study treatment, then RXC004 and nivolumab (if applicable) should be permanently discontinued.
Grade 3	If receiving RXC004 monotherapy; Interrupt RXC004. Manage as per Appendix J. When event has resolved to Grade 1 a and steroids tapered to $\leq 10$ mg of prednisone per day (or equivalent), resume RXC004 at a lower dose (see Table 15 for dose reduction scheme). If event re-occurs after re-starting study treatment, then RXC004 should be permanently discontinued.
Grade 4	If receiving RXC004 in combination with nivolumab; permanently discontinue both agents and manage as per Appendix J and Appendix G.  If receiving RXC004, either as monotherapy or in combination with nivolumab; Permanently discontinue study treatment (both agents if applicable) . Manage as per Appendix J and Appendix G

Event	Action
Dysgeusia events	
Grade 1/2	RXC004 related; Consider dose reduction, depending on clinical symptoms Manage as per Appendix I Interrupt RXC004 treatment if dysgeusia is associated with >5kg weight loss from baseline
Grade 2 associated with a 10-20% decrease in body weight	RXC004 related; Manage as per Appendix I Reduce RXC004 to a lower dose (see Table 15 for dose reduction scheme).
Grade 2 associated with a >20% decrease in body weight	RXC004 related; Permanently discontinue RXC004. Nivolumab can continue if clinical benefit is judged by investigator.
Other adverse events	
Any event that meets discontinuation criteria for nivolumab (see Appendix G)	Permanently discontinue nivolumab. RXC004 can continue if clinical benefit is judged by investigator.

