#### **9.4.3.3 Vital signs**

Vital signs data will be presented in listings. Abnormal vital signs values will be identified as those outside (above or below) the reference range. Vital signs data will be summarized using descriptive statistics.

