4.2.2 Visit Windowing

By visit summaries will be made considering the windows as below. The visit windowing is assessed relative to C1D1 date (not C0D1 due to delays between C0D1 and C1D1).

C0D1	C0D1
C1D1	(C1D1 - Day 8)
Day 15	(Day 9 - Day 21)
Day 29	(Day 22 - Day 42)
Day 57	(Day 43 - Day 70)

Day 85	(Day 71 - Day 98)
Day 113	(Day 99 - Day 126)
Day 141	(Day 127 - Day 154)
Day 169	(Day 155 - Day 182)
Day 197	(Day 183 - Day 210)
Day 225	(Day 211 - Day 238)
Day 253	(Day 239 - Day 266)
Day 281	(Day 267 - Day 294)
Day 309	(Day 295 - Day 322)
Day 337	(Day 323 - Day 350)
Day 365	(Day 351 - Day 378)
Day 393	(Day 379 - Day 406)
Day 421	(Day 407 - Day 434)
Day 449	(Day 435 - Day 462)
Day 477	(Day 463 - Day 490)

The following visits will not be remapped: Screening, IP Discontinuation, 30/90 Day Follow-up, Survival Follow-up.

In case several visits occur into the same windows the following rule is to be applied:

- For by-visit table, we will consider the mean of available assessments.
- For Shift table, we will consider either Minimum or Maximum available value depending on the direction.

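### Of the six vital signs, the SAP tabulates only blood pressure, in a shift table that cannot show direction, and plans none of the descriptive summaries (on-treatment weight included) that the protocol promises

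*SAP*

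**What the plan says.** **Protocol.** Section 9.4.3.3 plans listings, identification of values on either side of the reference range, and a summary: "Vital signs data will be summarized using descriptive statistics". Section 9.4.1 says what that means for continuous variables: n, mean, median, standard deviation, minimum and maximum. Section 8.3.5 also says vital signs will be summarised in the study report. It gives that as the reason for restricting when a deterioration is recorded as an adverse event. Weight is one of the vital signs in section 8.2.3. For RXC004-related dysgeusia, Table 14 attaches actions to weight loss, for example "Interrupt RXC004 treatment if dysgeusia is associated with >5kg weight loss from baseline". It has further rows for Grade 2 dysgeusia with a 10-20% or a >20% loss.

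**SAP.** Section 4.12.4.1 (Vital Signs) names weight, systolic and diastolic pressure, pulse, temperature and respiratory rate. It plans one table, "A shift table from baseline systolic blood pressure and diastolic blood to worst on-treatment results will be presented", and adds "Vital signs data and clinically relevant abnormalities in vital signs will also be listed". For the table, "The normal/abnormal classification will be made using the criteria defined in table below". Table 2 counts a systolic value as abnormal if below 80 or above 129 mmHg, and a diastolic value if below 60 or above 80 mmHg. Weight is summarised at baseline only (section 4.6).

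**The concern.** Two things look wrong. First, the SAP plans less than the protocol commits to: the descriptive statistics are absent, and pulse, temperature, respiratory rate and weight have neither an abnormality criterion nor a post-baseline summary. Second, the one table that is planned uses a two-class scale on a measurement that can go wrong in both directions, so it cannot separate falls from rises.

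Tolerability is a secondary objective, and the assessment of dysgeusia is part of its endpoint. Protocol 8.3.12 says CTCAE grade alone characterises dysgeusia poorly. Weight is the numerical measure that the protocol itself ties to that event. If it is not summarised, no planned table will show how much weight patients lost on treatment, and no planned table will show whether blood pressure moved down or up.

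**Working it through.** The plan states no figure to reproduce, so the check is a comparison of texts and a test of the Table 2 rule.

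**Step 1. Coverage of the six vital signs in SAP 4.12.4.1 and 4.6**

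| Vital sign | Baseline summary | Post-baseline table | Post-baseline descriptive statistics | Listing |
|---|---|---|---|---|
| Systolic pressure | no | shift | no | yes |
| Diastolic pressure | no | shift | no | yes |
| Pulse | no | no | no | yes |
| Temperature | no | no | no | yes |
| Respiratory rate | no | no | no | yes |
| Weight | yes | no | no | yes |

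The post-baseline count is 2 of 6 with a table and 0 of 6 with descriptive statistics. Protocol 9.4.3.3 makes no such distinction between vital signs.

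**Step 2. Is the change declared?** SAP 4.15 lists departures from the protocol. Its legible bullets move medical history and overall survival to listing only, which is the same kind of change. Vital signs are not mentioned in the legible text. One bullet is redacted.

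**Step 3. The Table 2 rule applied to systolic pressure (assumed values, normal band 80 to 129 mmHg)**

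| Baseline | On treatment | Cell in the shift table |
|---|---|---|
| 135 (abnormal, high) | 75 (abnormal, low) | abnormal to abnormal: no shift |
| 130 (abnormal, high) | 180 (abnormal, high) | abnormal to abnormal: no shift |
| 120 (normal) | 75 (abnormal, low) | normal to abnormal |
| 120 (normal) | 135 (abnormal, high) | normal to abnormal: same cell as the line above |

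With two classes, a patient already abnormal at baseline cannot register any worsening. A patient with both a low and a high value on treatment has no defined worst value.

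**Step 4. Do other SAP rules repair this?** The general rule in section 4.2.2 reads "For Shift table, we will consider either Minimum or Maximum available value depending on the direction". It deals with several visits falling in one window, assigns no direction to blood pressure, and does not split the Table 2 class. For laboratory shifts, section 4.12.3 does keep direction: "Low and/or High abnormal direction will be considered for each parameter". For QTcF, section 4.12.4.2 uses graded categories. Blood pressure has neither. Section 4.2.2 also sets windows for by-visit summaries, but nothing in 4.12.4.1 commits to a by-visit summary of vital signs.

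**Step 5. Can the adverse-event tables stand in for weight?** Under protocol 8.3.5 a vital-sign deterioration becomes an adverse event only if it is serious, is the reason for discontinuation, or is judged clinically relevant. SAP 4.12.1 then tabulates events by maximum grade. Loss that is not reported as an event reaches no table, and reported loss appears by grade, not in kg or percent.

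**Step 6. Is weight loss plausible here?** In protocol Table 10 (Phase 1 combination module), decreased weight was reported in 3/8 = 38% at RXC004 1.5 mg plus nivolumab and in 4/13 = 31% overall. Table 4 records one Grade 3 related weight loss among 6 DLT-evaluable patients at 1.5 mg monotherapy. These rates show that the event is expected. They do not measure the effect of the missing summary.

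**The case against.** The case on the other side has real content.

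- **The data are not lost.** All vital signs are listed, and SAP 4.2.5 includes scheduled and unscheduled measurements. With about 20 evaluable patients per arm, a reader can go through the listing. A reader might infer that the report will be unable to show weight loss or a fall in pressure. The documents do not support that: the values are unsummarised, not unreported.
- **Weight alone triggers nothing in the Table 14 dysgeusia rows.** Those rows require RXC004-related dysgeusia, and the two percentage rows require Grade 2. It would be too strong to say that weight as such drives RXC004 dosing.
- **Consequences are tabulated elsewhere.** SAP 4.10.1 counts dose reductions and interruptions with reasons. Section 4.12.1 tabulates events leading to them and events by maximum grade. Section 4.12.2 adds dysgeusia charts. Protocol 8.3.5 names dose adjustment or interruption among the considerations for clinical relevance, so weight loss that altered dosing should often be reported as an event. This narrows the gap but leaves it open, because the size of loss is still not summarised and reporting depends on judgement.
- **Merging low and high is not in itself a breach of the protocol.** Section 9.4.3.3 also defines abnormal in either direction and promises no separate shift tables. That is correct. The objection to Table 2 is that the resulting table is uninformative. The departure from the protocol is the missing descriptive statistics.
- **No blood-pressure signal is documented.** The RXC004 risk section names none, and the values in the check are illustrative.
- **Non-declaration cannot be proved.** A reader might infer that the summaries were dropped without a declaration. The redacted bullet in SAP 4.15 prevents that conclusion.

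**Conclusion.** The point holds, and it is minor. The protocol commits to descriptive summaries of vital signs. The SAP plans a shift table for two of six and descriptive statistics after baseline for none. The shift table cannot distinguish a fall from a rise, and it hides any worsening from an abnormal baseline. On-treatment weight, which together with RXC004-related dysgeusia is a dose-modification criterion, has no planned summary.

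The effect is confined to the clarity of safety reporting. No estimate, test or primary endpoint changes, and no clinical rule is in question. The conclusion rests on two assumptions: that the redacted bullet in SAP 4.15 does not concern vital signs, and that no table specification outside these documents adds the summaries. If either is wrong, the complaint about missing summaries shrinks, but the Table 2 problem remains.

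**What to change.** In SAP 4.12.4.1:

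1. Classify systolic and diastolic pressure as low, normal or high with the existing Table 2 limits. Tabulate the shift from baseline to the on-treatment minimum and, separately, to the on-treatment maximum, in line with the laboratory shifts in 4.12.3.
2. Add by-visit descriptive statistics (value and change from baseline) for all six vital signs, with percentage change for weight, using the windows already in 4.2.2.
3. Tabulate each patient's maximum weight loss at the cut-offs already in protocol Table 14 (>5 kg, 10-20%, >20%), for all patients and for those with RXC004-related dysgeusia. The overall count includes loss from any cause; the subgroup count is closer to the protocol criterion. Count the kg and percentage cut-offs separately, because they coincide only at a baseline weight of 5 / 0.10 = 50 kg.

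If the sponsor prefers listings for items 2 and 3, SAP 4.15 should state that the protocol's summaries are dropped and why.

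The cost is a few extra standard tables from data already collected. No extra visits, measurements or patients are needed.

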4.12.4.1 CCI

Blood samples for CCI will be obtained from patients at timepoints specified in the SoA. Summary statistics of values and relative change from baseline by visit will be presented for CCI values.

By-patient listing will be provided for all patient in FAS by visit, including values and changes from baseline.

4.12.4.2 Electrocardiograms (ECG)

Trippleate 12-lead ECGs will be performed at timepoints as specified in the SoA (see protocol). ECGs should be obtained after the patient has been in a supine position for 5 minutes and recorded while the patient remains in that position. Mean QT intervals corrected for heart rate should be calculated using Fridericia's formula (QTcF). The following variables will be collected:

- PR Interval (msec)
- RR Interval (msec)
- QRS Complex (msec)
- QT Interval (msec)
- QTcF interval (msec)

Mean of the 3 measures (considering 1 decimal) will be considered at each timepoint (Pre-dose, 1-hour dose, 12-hour dose).

ECGs will be performed 3 times and an overall evaluation will be provided, as follows:

- Overall ECG evaluation (normal, abnormal – not clinically significant, abnormal – clinically significant)

A shift table of baseline QTcF to worst on-treatment results will be presented. For rating the worst on-treatment value, the following categories will be used based on the varying degrees of abnormality above, in the order of least to most severe (top to bottom):

- Missing result
- <=450 msec (i.e. ‘normal’)
- >450-<=480 msec
- >480-<=500 msec
- >500 msec

Baseline QTcF will be the pre-dose value at baseline. Worst on-treatment QTcF will be the worst post-baseline all timepoints considered.

All ECG parameters will be listed.

4.12.4.3 Performance Status

Eastern Cooperative Oncology Group (ECOG) Performance Status will be assessed at the times specified in the SoA based on the following (see protocol):

0. Fully active; able to carry out all usual activities without restrictions
1. Restricted in strenuous activity, but ambulatory and able to carry out light work or work of a sedentary nature (e.g. light housework or office work)
2. Ambulatory and capable of self-care, but unable to carry out any work activities; up and about more than 50% of waking hours
3. Capable of only limited self-care; confined to bed or chair more than 50% of waking hours
4. Completely disabled; unable to carry out any self-care and totally confined to bed or chair
- 5 Dead

A shift table will be presented to show worst changes from baseline separately for arm A and arm B. ECOG score results (including screening value) will be listed by arm and visit.

4.12.4.4 Bones Evaluation

Blood Sample for **CCI** and DXA scan assessments will be performed at timepoints as specified in the SoA (see protocol). The following variables will be collected:

- **CCI**

CCI

CCI

CCI

CCI

CCI

CCI

Bones Evaluation variables will also be listed.

CCI

4.12.4.5 Physical Examination

Physical Examination will be assessed at the times specified in the SoA. By-patient listing will be provided for all patient in FAS by visit, including details in abnormalities if any.

4.12.5 Safety Monitoring Committee

A safety monitoring committee (SMC) will be appointed to review safety data from patients in this study and a second study of RXC004 in patients with pancreatic and biliary tract cancer (RXC004/0003).

The SMC is a group consisting of the country principal investigators (PI) from each of the phase 2 studies and a statistician. An independent bone metabolism consultant will review the data and provide expert advice to the SMC meetings, but will not be a formal member of the SMC.

The SMC will be convened to review the safety and tolerability of RXC004 at regular intervals.

The safety reviews will start when approximately **█** patients across the phase 2 clinical trial program have been dosed for at least 1 cycle of study treatment and will continue every 6 months until the phase 2 studies close or last patient discontinues study treatment (whichever occurs first). Additional safety reviews may be performed at other times as deemed appropriate by the Sponsor.

Since the studies are open label, there are no blinding issues associated with performing interim safety reviews. Full details of the SMC procedures, processes, and analyses can be found in the SMC Charter.

4.13 Exploratory Objectives

CCI

4.14 Determination of Sample Size

The method by Frewer et al [10], together with the totality of the data collected, will be used to guide go/no-go decision making:

For the combination RXC004+nivolumab arm, assuming a CCI % response rate which is considered to be clinically significant in the target population, against a reference value of CCI% response rate (Eng C et al 2019) as CCI, then a sample size of 20 achieves greater than CCI% power, at the CCI

CCI

CCI

These hurdles

will be used to guide the decision for onward development. The totality of the data, including the results from the secondary endpoints will be used to in the final decision.

For the monotherapy RXC004 arm, assuming a CCI % disease control rate which is considered to be clinically significant in the target population, against a reference value of CCI% DCR [11 - 12] as a CCI, then a sample size of 20 achieves greater than CCI% power, at the CCI

CCI

CCI

CCI

These hurdles

will be used to guide the decision for onward development. The totality of the data, including the results from the secondary endpoints will be used to in the final decision.

Approximately CCI patients are expected to be enrolled in order for approximately 20 patients to be in the evaluable dataset in each treatment arm.

4.15 Changes in the Conduct of the Study or Planned Analysis

In order to make the most appropriate assessment of efficacy for the compound and not be influenced by early dropouts not due to drug the Evaluable set will require at least 4 weeks of RXC004 intake

and at least one post dose radiographic tumour assessment or progressed/died ahead of the first radiographic assessment instead of one single dose as initially planned.

After an ongoing review of the available data the following changes to the final outputs were made compared to the protocol

- Medical History will not be summarized but will be listed.
- CCI [REDACTED]
- Overall Survival will not be summarized but will be listed.

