1.5 mg QD RXC004 + nivolumab 480 mg q4w	8	6 e	
Tolerated dose
 
Events <math>\geq</math> Grade 2 in DLT evaluable patients (4/6 patients):
 
G2 dysgeusia (2/6 patients) b
 
G2 diarrhoea (1/6 patients) b
 
G2 diarrhoea (1/6 patients) c
 
G2 reduced appetite (1/6 patients) b
 
G2 nausea (1/6 patients) b
 
G2 constipation (1/6 patients) d
 
G2 anorexia (1/6 patients) b
 
G2 increased total bilirubin (1/6 patients) b
 
G2 High TBL (1/6 patients) b
 
G3 DILI (1/6 patients) [DLT] c

a The DLT assessment period runs from the start of dosing with RXC004 (Cycle 0 Day 1) up to Cycle 1 Day 28. To be evaluable for DLT assessment patient must had received  $\geq$  66% of the intended dose of RXC004 and all of the nivolumab infusion during Cycle 1, or have experienced a DLT event in the assessment period.

b Related to RXC004.

c Related to RXC004 and nivolumab.

d Related to nivolumab.

e Two of the 8 patients who received RXC004 1.5 mg in combination with nivolumab discontinued prior to the end of Cycle 1 without meeting DLT criteria, and were replaced.

AE, adverse event; CTCAE, Common Terminology Criteria for Adverse Events; DLT, dose-limiting toxicity; q4w, every 4 weeks; QD, once daily.

A summary of the treatment-emergent adverse events (TEAEs) reported in Module 2 (RXC004 + nivolumab combination therapy) up to 01 July 2022 is presented in Table 9.

**Table 9      Summary of Treatment-Emergent Adverse Events as of 01 July 2022,  
Phase 1 study RXC004/0001 (RXC004 + Nivolumab Module 2)**

Number of patients with:	RXC004 1.0 mg + nivolumab (N=5)	RXC004 1.5 mg + nivolumab (N=8)	Overall (N=13)
TEAE	5 (100)	8 (100)	13 (100)
Treatment-Related TEAE	5 (100)	8 (100)	13 (100)
RXC004-Related TEAE	5 (100)	8 (100)	13 (100)
Nivolumab-Related TEAE	3 (60)	6 (75)	9 (69)
TEAE $\geq$ Grade 3	3 (60)	4 (50)	7 (54)
Treatment-Related TEAE $\geq$ Grade 3	1 (20)	3 (38)	4 (31)
RXC004-Related TEAE $\geq$ Grade 3	1 (20)	3 (38)	4 (31)
Nivolumab-Related TEAE $\geq$ Grade 3	0 (0)	2 (25)	2 (15)
TEAE $\geq$ Grade 4	0 (0)	0 (0)	0 (0)
Treatment-Related TEAE $\geq$ Grade 4	0 (0)	0 (0)	0 (0)
Serious TEAE	3 (60)	3 (38)	6 (46)
Serious Treatment-Related TEAE	0 (0)	1 (13)	1 (8)
Serious RXC004-Related TEAE	0 (0)	1 (13)	1 (8)

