## **6.6 Dose Modification**

RXC004 dose reduction and interruption are permitted. Nivolumab dose reduction is not permitted but dose interruption/delay is permitted as per Appendix G.

RXC004 may be dose interrupted (withheld) until a clinically significant (any grade) and/or a grade  $\geq 3$  related adverse event resolves to baseline or  $\leq$  grade 2. RXC004 may also be withheld if it is necessary to give a concomitant medication that is a moderate or strong CYP3A4 inhibitor. RXC004 related colitis events should be managed as per Appendix J.

Adverse events that are assessed as being causally related nivolumab should be managed as per the Nivolumab Toxicity Management and Dose Modification Guidelines (Appendix G). If either agent is interrupted or discontinued for a related-AE the other agent (nivolumab or RXC004) may be continued if the patient is judged (by the investigator) to be receiving clinical benefit.

RXC004 and nivolumab dose interruption and stopping criteria are detailed in Table 14.

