### **9.4.2 Efficacy**

#### **9.4.2.1 Primary Endpoint(s)**

The primary endpoint for the monotherapy arm is disease control rate and the primary endpoint for the combination arm is the objective response rate, both based on a individuals best overall response using investigator RECIST 1.1 assessments.

Objective response rate is defined as the proportion of subjects with a best overall response of complete response or partial response, based on local investigator assessment, as defined in RECIST 1.1. Confirmation of response is required for declaring PR or CR as the BOR. A confirmed response is defined as a CR or PR followed by a CR or PR a least 4 weeks later. The ORR will be summarised with accompanying 90% confidence interval calculated using the Clopper Pearson method. This will be calculated on the full analysis set and the evaluable analysis set with the evaluable analysis set calculation being considered primary. In the summary tables the incidence of unconfirmed responses will be presented as well as the patients with confirmed responses.

Disease control rate (DCR) is defined as the proportion of patients with a BOR of either CR, PR or stable disease (SD) for at least 16 weeks post baseline (corresponding to SD for 2 scheduled scans post baseline). A time window of 1 week around the week 16 visit will be applied. The DCR and associated 90% confidence interval, calculated using the Clopper Pearson method will be presented. This will be calculated on the full analysis set and the evaluable analysis set with the evaluable analysis set calculation being considered primary.

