4.5 Analysis Sets

A summary of the number of patients included in each analysis population described below will be provided for arm A and arm B. Percentage of subjects in the evaluable set will be calculated based on the full analysis set (FAS).

A listing of patients included into each of the analysis set will be presented will be provided. The patients who did not meet the eligibility criteria or were screen failures will also be listed.

- **Full analysis set (FAS) / Safety analysis set:** All patients who enrolled and received at least one dose of study drug (RXC004 in the case of the monotherapy arm and at least one of RXC004 or nivolumab in the combination arm).

- CCI [REDACTED]

- **PK analysis set:** All patients in the safety analysis set who have had at least 1 blood sample.

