4.11.2 Primary Efficacy Variable(s)

All primary efficacy analyses will be conducted on the evaluable set.

Primary objective of study will consider the overall tumour response provided by Investigators. A listing containing information on target, non-target lesions, new lesions, overall response will be provided (ordered by arm, patient and visit).

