4.11.3 Secondary Efficacy Variables

All secondary efficacy analyses will be conducted on the FAS and, where appropriate, on the evaluable set.

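### The four-week RXC004 rule in SAP 4.15 also removes early related-toxicity stops from the primary DCR and ORR, which goes beyond its stated aim

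*SAP*

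**What the plan says.** SAP 4.15 states both purpose and rule: the assessment should "not be influenced by early dropouts not due to drug the Evaluable set will require at least 4 weeks of RXC004 intake". A post-dose radiographic assessment is also needed. The alternative route into the set is for patients who have progressed or died early: "or progressed/died ahead of the first radiographic assessment instead of one single dose as initially planned". The formal definition (Protocol Table 18, SAP 4.5) is redacted, so 4.15 is the only visible wording.

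SAP 4.11.2 says "All primary efficacy analyses will be conducted on the evaluable set". Protocol 9.4.2.1 asked for more, for both ORR and DCR: "This will be calculated on the full analysis set and the evaluable analysis set with the evaluable analysis set calculation being considered primary". SAP 4.11.3 keeps the full analysis set (FAS) for the other endpoints: "All secondary efficacy analyses will be conducted on the FAS and, where appropriate, on the evaluable set". The FAS is "All patients who enrolled and received at least one dose of study drug". SAP 4.14 plans enrolment to yield about 20 evaluable patients per arm and ties that number to the go/no-go hurdles.

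Two conduct rules matter. Under Protocol 7.1 and the schedules of assessments, a patient who stops for a reason other than progression continues to be assessed for progression. Under Protocol 6.6, "If either agent is interrupted or discontinued for a related-AE the other agent (nivolumab or RXC004) may be continued" if the investigator sees benefit.

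**The concern.** The purpose is selective and the rule is not. The purpose concerns losses that say nothing about the drug. The rule tests only time on RXC004 and whether a scan, progression or death was recorded. A patient who cannot stay on RXC004 for four weeks because of its toxicity is informative about the regimen, and in an activity analysis would normally count as a non-responder. The rule takes that patient out of the denominator.

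This set is primary for both arms, and enrolment is sized to reach 20 evaluable patients, so early toxicity failures would leave the denominator while enrolment aims to fill it with others. The visible SAP also has no explicit FAS version of DCR for Arm A or ORR for Arm B that would show the difference. The evaluable definition was revised in SAP versions 3.0 and 4.0 of an open-label study, which makes a loosely targeted exclusion harder to defend.

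**Working it through.** **1. What the visible rule does.** The conjunctions in 4.15 are not bracketed, so there are two readings.

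- Reading 1: (at least 4 weeks and a scan) or progression/death before the first scan.
- Reading 2: at least 4 weeks and (a scan or progression/death before the first scan).

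| Patient | Reading 1 | Reading 2 |
|---|---|---|
| Stops week 3, unrelated reason, no scan | out (intended) | out (intended) |
| Stops week 3, related toxicity, no scan, progression or death | out | out |
| Stops week 3, related toxicity, week-8 scan shows progression | out | out |
| Progresses or dies at week 3 | in | out |
| Stops week 6 for toxicity, week-8 scan done | in | in |

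The second and third rows are the mismatch, and they hold under both readings. In the third row, progression occurs at the first scan, not before it, so the alternative route does not apply.

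**2. Can such patients arise?** Protocol Table 14 requires permanent discontinuation for related Grade 4 toxicity and for Grade 3 colitis on the combination, with no minimum time on drug. So they can. How often is not stated.

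**3. Effect on the rate.** Let N be the number treated, x the successes, k the number dropped (all failures), and q = k/N. Then

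evaluable rate = x/(N-k) = (x/N)/(1-q).

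Exact two-sided 90% Clopper-Pearson intervals, the SAP's method:

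| Illustration | All treated | Evaluable only |
|---|---|---|
| ORR, k = 5, q = 5/25 = 20% | 4/25 = 16.0% (5.7 to 33.0) | 4/20 = 20.0% (7.1 to 40.1) |
| DCR, k = 3, q = 3/23 = 13% | 13/23 = 56.5% (37.5 to 74.2) | 13/20 = 65.0% (44.2 to 82.3) |

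The counts x and k are assumptions.

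**4. What is known about q.** Protocol Tables 5 and 9 give treatment-related discontinuation in Phase 1, at any time: 0/6 at 2 mg monotherapy (exact 90% interval 0 to 39%) and 2/8 at 1.5 mg with nivolumab (5 to 60%). Neither count is limited to the first four weeks. Table 8, footnote e, adds that "Two of the 8 patients who received RXC004 1.5 mg in combination with nivolumab discontinued prior to the end of Cycle 1"; it goes on to say that they had not met DLT criteria and were replaced, and it gives no reason. So q is not available from the documents.

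**5. Sensitivity of a go rule.** The plan's power cannot be reproduced, because p0, p1, alpha and the hurdles are redacted. As an assumption, take p0 = 40% for DCR and 5% for ORR (Protocol 2.3.3 gives about 40% and below 5% for current third-line agents). Take as the rule the smallest count out of 20 with exact one-sided error at or below 0.05: 13 for DCR and 4 for ORR. The probability of reaching it when the all-treated rate equals p0 is P(X >= r), with X binomial (20, p0/(1-q)):

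- DCR, at least 13/20: 0.021 at q = 0; 0.033 at 5%; 0.052 at 10%; 0.083 at 15%.
- ORR, at least 4/20: 0.016 at q = 0; 0.023 at 10%; 0.041 at 25%.

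**The case against.** The strongest reply is that the operative definition is redacted. Section 4.15 summarises a change, and SAP 4.5 may deal with toxicity stops. That stands, and it makes the point conditional on the visible text.

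A requirement for adequate RXC004 exposure is also a coherent choice when the aim is the compound's activity. That would justify an exposure-based set described as such. It does not reconcile the rule with the purpose 4.15 gives for it.

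The affected patients may be few. A first related Grade 3 event generally leads to interruption and resumption at a lower dose (Protocol Tables 14 and 15), and Phase 1 had no related Grade 4 or 5 events up to 2 mg monotherapy and no Grade 4 or higher event on the combination. This limits the size.

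There are safeguards: 4.15 does not visibly withdraw the protocol's FAS analysis, set membership and reasons for ending treatment are reported, and the hurdles only guide a decision on the totality of data. These reduce the consequence, but they do not correct the primary denominator.

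Three stronger readings are tempting and are not supported:

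- A reader might infer that the primary rates omit treatment failures in general. Under the natural reading (Reading 1), patients who progress or die before the first scan stay in, and so do toxicity stops after week 4 with a scan.
- A reader might take the two early Phase 1 stops as evidence of a 25% early toxicity rate, and apply it to Arm A's DCR. Their reasons are not given, they were on the Arm B regimen, and 2 mg monotherapy had 0/6 discontinuations.
- A reader might infer upward bias from Arm B patients who stop RXC004 but continue nivolumab. Such a patient could respond, so dropping them has no fixed direction.

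**Conclusion.** The mismatch is real on the visible text. A rule meant for losses unrelated to the drug also removes related-toxicity stops before week 4, including one whose first scan shows progression, and it does so under either reading of the sentence. If those removed are all failures, the primary rates are inflated by 1/(1-q). An occasional excluded patient with durable stable disease or a confirmed response off drug would reduce or reverse this.

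The size is unknown because q is unknown: a few percentage points in the ORR illustration, about eight in the DCR illustration, and none if no such patient occurs. The point should be fixed, but it does not invalidate the analysis. It falls away if the redacted definition already keeps these patients.

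**What to change.** First check SAP 4.5 for an existing exception. If there is none, amend 4.5 and 4.15:

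- A patient with less than 4 weeks of RXC004 is non-evaluable only if the documented reason for stopping is unrelated to study drug and there is no post-dose scan, progression or death.
- Patients who stop for related toxicity, and anyone with documented progression, stay in the denominator with their observed best overall response, or as non-responders if there is none.
- Arm B patients who stop RXC004 for toxicity and continue nivolumab follow the same rule.
- Bracket the sentence so that it has one reading.
- Report the protocol's FAS results for DCR (Arm A) and ORR (Arm B) beside the evaluable-set results.

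The cost is one SAP paragraph and two additional results, with no new data. The rates may be slightly less favourable. The denominator would also depend on a recorded stop reason, which is a judgement in an open-label study; the FAS result, which does not depend on it, offsets that.
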